COMPARISON OF OPTIC NERVE SHEATH DIAMETERS MEASURED BY OPTIC ULTRASONOGRAPHY BEFORE AND AFTER LUMBAR PUNCTURE IN IDIOPATHIC INTRACRANIAL HYPERTENSION PATIENTS

01 April 2014

Patient Selection Criteria

Patients who apply to the neurology outpatient clinic of Ankara Numune Training and Research Hospital between May 2014 and December 2015 with the pre-diagnosis of IIH will be included in the study. In order to determine normal ONSD measurement, who apply to the neurosonology unit for other complaints (dizziness, cerebrovascular accident, transient ischemic stroke, patent foramen ovale examination etc.) than headaches will be included as the control group after they signing the consent form and their ONSD will be measured. All the patients participating in the study will be informed about the method and the aim of the study. All cases will sign the informed consent form. For the patient group, individuals who will be diagnosed with IIH according to Modified Dandy criteria aged 17-65 having no contraindications for lumbar puncture, who accept the intervention and had no additional neurological or ocular disease; and for the control group, individuals who aged 17-65 and apply with other complaints than headaches, visual impairment or tinnitus will be included in the present study.

Cranial MRI will be obtained from patients in order to eliminate other factors that can cause ICP and to avoid intracranial LP contraindications. Evaluations will be made in terms of conditions that can create contraindications for the administration of lumbar puncture (intracranial mass, general condition disorder, thrombocytopenia or other haemorrhage problems, infection in the LP area, severe skeletal dysplasia). The patients' medical history including age, height, weight and body mass indices will be recorded. The study was approved by the Ethical Committee of our hospital.

Body Mass Index Evaluation

Body mass indices will be calculated using the formula "Body Weight (kg)/ Height in meters squared (m^2)". According to this formula, individuals with a BMI of <20 are categorized as underweight, 20-25 as normal weight, 25-30 as overweight and >30 as obese. However, while comparing the data in our study, we will evaluate the patients in two groups as BMI <30 non-

obese and BMI >30 obese. In our study, CSF opening pressure limit value will be accepted as 200 mm H₂O (CSF) in patients with BMI <30 and as 250 mm H₂O (CSF) in those with BMI >30, that is, in obese patients.

Optic Nerve Ultrasonography

Measurements will be taken from all the patients before and 10-15 minutes after the LP by a neurosonologist experienced in ONSD measurement, have no prior information about the patients' clinical characteristics and who will not participate in the LP administration or treatment decision of the patients. A high resolution (Toshiba Xario Model SSA-660A, Japan) ultrasonography device and a 7.5 MHz linear probe will be used for the measurements. After making depth and gain adjustments, carotid-vertebral artery ultrasonography will be adjusted, and MI (mechanical index) will be reduced in accordance with the international rules. The patients will be told to look forward with their eyes closed in supine position and gel will be applied to both eyes. As described in the literature, ONSD measurements will be taken twice from the border surrounded by the hyperechogenic intraorbital fat tissue of the hypoechogenic nerve sheath surrounding the hyperechogenic area around the optic nerve (overall sheath diameter) of both eyes at 3 mm under the bulb from the sections that give the best images of the area where optic nerve enters into the globe by rotating clockwise and the measurements will be recorded on the axial and sagittal planes.

Lumbar Puncture Procedure

After measurements will be obtained before LP, the patient will be placed in the lateral decubitus position. All the patients will be given 20 mg of subcutaneous prolicaine for local anaesthesia. Over the line drawn from the superior iliac spina border, spinous processes will be examined and following the sterilization with povidone-iodine, subarachnoid space will be entered using an 18Gx90 mm LP needle from the appropriate distance. Once the CSF will be seen to be coming out, CSF opening pressure measurement will be taken with an LP manometer. After measuring the opening pressure, approximately 15-20 ml of CSF will be taken as sample for the laboratory examinations; later the CSF closing pressure will be measured, and the administration will be finalized by taking the needle out. The patient will be rolled back to the supine position. Ultrasonographic measurements will be taken again 10-15 minutes after the LP administration. Similarly, USG and ONSD measurements will be obtained from the control group in supine position without LP.

Statistical Analyses

The data will be given as mean \pm SD and put into analysis on SPSS (23.0) package program. For all the tests, values under the p value of 0.05 will be accepted as statistically significant. Chi square test, independent sample test, paired sample test and Pearson correlation analyses will be carried out for the evaluation of the data. Statistical numeric data will be rounded off to have a single digit after the decimal point.

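### The IIH-versus-control ONSD comparison has no stated protection against imbalance in age, sex or BMI, so it is open to uncontrolled confounding

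*Combined protocol and SAP*

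**What the plan says.** Patient Selection Criteria gives the purpose and source of the control group: "In order to determine normal ONSD measurement, who apply to the neurosonology unit for other complaints". The examples are "dizziness, cerebrovascular accident, transient ischemic stroke, patent foramen ovale examination etc.) than headaches will be included as the control group". Cases are recruited from the neurology outpatient clinic with a pre-diagnosis of IIH.

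The eligibility rule for controls is "for the control group, individuals who aged 17-65 and apply with other complaints than headaches, visual impairment or tinnitus will be included". Apart from consent, nothing further is required of them. No matching, quota or balancing on age, sex or BMI is described.

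On data collection the same section says "The patients' medical history including age, height, weight and body mass indices will be recorded". Sex is not named.

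Body Mass Index Evaluation plans one split by body build: "while comparing the data in our study, we will evaluate the patients in two groups as BMI <30 non"-obese against obese. The same section ties the opening-pressure limit to BMI.

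Statistical Analyses lists the methods in one sentence, "Chi square test, independent sample test, paired sample test and Pearson correlation analyses will be carried out for the evaluation of the data", with the threshold that "values under the p value of 0.05 will be accepted as statistically significant". No test is assigned to a named comparison. No sample size, ONSD standard deviation or expected group difference is given.

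**The concern.** The control group is the only source of a normal ONSD value in this study. That value is useful for judging IIH patients only if controls resemble them in whatever else affects ONSD. The two groups arrive by different referral routes, and a shared age range of 48 years (65 − 17) does not balance age within it. The plan itself treats body build as relevant, since it classifies patients by BMI and uses BMI to set the pressure limit.

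If the groups differ in age, sex or BMI, and any of these is related to ONSD, an unadjusted difference in means combines the IIH effect with the covariate effect. A larger sample does not help: the bias stays the same while the standard error shrinks, so a false rejection becomes more likely. If the covariates were not collected in controls, the problem may not be repairable afterwards.

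**Working it through.** **1. Reading the text.** The plan states no figure for this comparison, so there is none to reproduce. The check is whether any provision would prevent or remove an imbalance.

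| Possible protection | What the plan provides |
|---|---|
| Same source population | No: outpatient clinic versus neurosonology unit |
| Matching or quotas | None stated |
| Covariates recorded in both groups | Not explicit: worded for patients, sex not named |
| BMI split at 30 | Worded for patients; not tied to the case-control contrast; does not address age or sex |
| Adjusted analysis | None listed |

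A chi-square test can display an imbalance in a categorical covariate. A Pearson coefficient can show that a covariate tracks ONSD. Neither produces an adjusted group difference.

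**2. Illustration in millimetres (BMI only).** All inputs are assumptions: slope 0.01 to 0.03 mm per kg/m², BMI gap 5 to 8 kg/m², ONSD SD 0.5 or 0.7 mm, 30 or 50 per group, two-sided 5% test (the plan does not state sidedness), and no true IIH effect.

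Bias = slope × gap: from 0.01 × 5 = 0.05 mm to 0.03 × 8 = 0.24 mm.

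The rejection probability comes from the noncentral t with noncentrality bias / (SD × √(2/n)). For example, 0.24 / (0.5 × √(2/30)) = 1.86, which gives 44.8%.

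| SD (mm) | n per group | Bias 0 | Bias 0.05 mm | Bias 0.24 mm |
|---|---|---|---|---|
| 0.5 | 30 | 5% | 6.7% | 44.8% |
| 0.5 | 50 | 5% | 7.9% | 66.1% |
| 0.7 | 30 | 5% | 5.9% | 25.7% |
| 0.7 | 50 | 5% | 6.4% | 39.7% |

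**3. Illustration for any one covariate.** Let the covariate differ by d SD between groups and correlate r with ONSD within groups (both assumed). The spurious difference is r × d within-group SDs. By normal approximation,

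P(reject) = Φ(z − 1.96) + Φ(−z − 1.96), with z = r × d / √(2/n).

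At 40 per group and d = 1:

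| r | z | P(reject) |
|---|---|---|
| 0 | 0 | 5% |
| 0.1 | 0.45 | 7% |
| 0.2 | 0.89 | 15% |
| 0.3 | 1.34 | 27% |
| 0.5 | 2.24 | 61% |

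Over n = 20 to 60, r = 0.1 to 0.5 and d = 0.5 to 1.5, the range is 5.3% to 98%.

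**4. Effect of adjustment.** In a simulation of 4,000 runs per setting at 40 per group, with the covariate in a linear model:

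| r, d | Unadjusted | Adjusted | Variance ratio, adjusted to unadjusted |
|---|---|---|---|
| 0.3, 1.0 | 26% | 5.0% | 1.15 |
| 0.2, 1.0 | 13% | 5.0% | 1.21 |
| 0.3, 1.5 | 52% | 4.9% | 1.45 |
| 0, 1.0 | 4.8% | 5.4% | 1.26 |

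The unadjusted rates differ slightly from step 3 because of simulation error and the use of t rather than normal quantiles. Over the first three rows the interval widens by a factor of √1.15 = 1.07 to √1.45 = 1.20. The last row shows the cost of adjusting for a covariate that turns out not to matter.

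**The case against.** **Confounding is not demonstrated.** This stands. A reader might infer that the IIH-control difference is confounded. The documents give no age, sex or BMI distribution for either group and no association of any of them with ONSD. Different referral routes make imbalance plausible, no more.

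**No test is tied to this contrast.** This also stands. A reader might infer that an unadjusted independent-samples test is the only planned group comparison. The list assigns no test to anything, and that test could equally serve the obese versus non-obese contrast among patients. What remains is that it is the only listed test suited to a difference in mean ONSD between two separate groups, and it does not adjust.

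**The recording gap may be one of wording.** In part. The plan sometimes uses the word patients broadly enough to cover everyone enrolled, and its list of recorded items is introduced as non-exhaustive. It would be wrong to conclude that sex, height and weight will not be collected in controls. But the neighbouring sentences concern MRI and puncture, which apply to cases, so collection in controls is not assured.

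**The title objective is before versus after lumbar puncture.** Correct. Each patient is compared with himself or herself minutes apart, so age, sex and BMI cannot confound that result. A reader who took this point to undermine the study's main comparison would be mistaken.

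**The illustrations settle little.** They show that the problem can range from nothing to serious. They treat one covariate at a time, assume no IIH effect and do not set the bias against a plausible IIH effect. Imbalances in different covariates could add up or offset each other. The case for change rests on the missing safeguard, not on a predicted bias.

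**Conclusion.** The concern holds in a limited form. The IIH-versus-control comparison of ONSD, and any normal value taken from the controls, is open to uncontrolled confounding by age, sex and BMI, because neither the selection rule nor the listed analyses guard against it and the data needed for adjustment are not clearly secured in controls. The plan's BMI split does not fill the gap.

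The size cannot be derived from the documents. Every rate in the working depends on assumed slopes or correlations, group gaps, SDs and sample sizes, and with no covariate-ONSD association the error rate stays at 5%. The before/after comparison is untouched. This is a change the sponsor should make, ideally before controls are enrolled, but it does not call the titled objective into question.

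**What to change.** 1. In Patient Selection Criteria, state that age, sex, height and weight are recorded for every case and every control.
2. In Statistical Analyses, name the case-control contrast of pre-puncture ONSD and analyse it with a linear model containing group, age, sex and BMI. Report the adjusted difference with its 95% CI as the main estimate and the unadjusted difference as descriptive.
3. Tabulate age, sex and BMI by group and check overlap. Where cases have few comparable controls, the model extrapolates, and the report should say so. The model also assumes the same BMI slope in both groups. Since the opening-pressure limit for cases depends on BMI, plot ONSD against BMI by group before relying on that.
4. Where feasible, steer control recruitment towards a broadly similar mix of sex, age and obese/non-obese status. Full cell matching should not be required: two sexes × five 10-year bands × two BMI groups make 20 cells, or 30/20 = 1.5 controls per cell at an assumed 30 controls.

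The cost is about a minute of extra data per control and a somewhat wider interval. Optional balancing may slow control recruitment, particularly if some combinations are scarce among neurosonology attendees. The model runs in the named package, and no extra procedure is needed.

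### The plan compares patients by BMI below versus above 30 although BMI is held as a number; use continuous BMI in the BMI analyses and assign a BMI of exactly 30

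*Combined protocol and SAP*

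**What the plan says.** All BMI rules are on the opening pages of the combined protocol and SAP.

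- **Collection.** Under Patient Selection Criteria, the patients' "medical history including age, height, weight and body mass indices will be recorded". Under Body Mass Index Evaluation, "Body mass indices will be calculated using the formula" for weight over height squared. BMI is therefore available as a number for each patient.
- **Descriptive classes.** "individuals with a BMI of <20 are categorized as underweight, 20-25 as normal weight, 25-30 as overweight and >30 as obese".
- **Use in comparisons.** The next sentence turns away from those classes: "while comparing the data in our study, we will evaluate the patients in two groups as BMI" below 30, called non-obese, and above 30, called obese ("obese and BMI >30 obese").
- **CSF opening pressure limit.** The same cut sets the limit: 200 mm H₂O for BMI below 30, and 250 mm H₂O "in those with BMI >30, that is, in obese patients".
- **Tests.** The Statistical Analyses section lists chi-square, independent-sample, paired-sample and Pearson correlation analyses at p below 0.05. It assigns no variable to any of them.

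**The concern.** The one sentence that says how BMI enters a comparison replaces a measured quantity with a two-level label. A cut at 30 is needed to assign the pressure limit, but that is no reason to analyse BMI through the same cut. Splitting treats a patient just above 30 like one far above it, and treats patients either side of 30 as wholly different. Any real gradient of ONSD, ONSD change or opening pressure with BMI then becomes harder to detect, and nothing is gained in return.

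Two further matters follow from the same sentences. First, neither the grouping nor the pressure limit covers a BMI of exactly 30. Second, if the pressure limit governs who is diagnosed, patients are selected at different pressures on either side of 30, and this shapes any contrast between obese and non-obese patients.

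**Working it through.** The plan gives no sample size, effect size or BMI distribution, so it has no figure to reproduce. What follows is illustrative, with each assumption marked.

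**1. Information kept by the split.** Assume BMI is normal and the outcome is linear in BMI. Let p be the share of patients on one side of 30 and z the standard normal quantile of p. The efficiency of the split relative to continuous BMI is E = φ(z)² / [p(1 − p)].

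| Split at 30 (assumed) | φ(z) | E | Information lost | Sample size inflation 1/E |
|---|---|---|---|---|
| 50:50 | 0.399 | 0.637 | 36% | 1.57 |
| 70:30 | 0.348 | 0.576 | 42% | 1.74 |
| 80:20 | 0.280 | 0.490 | 51% | 2.04 |

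The 50:50 row is the best case under normality: E = 2/π, a loss of 36.3%. The formula is symmetric, so it does not matter which side is larger.

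**2. Other shapes of BMI.** E is the squared correlation between BMI and its two-group version.

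- Right-skewed (lognormal, log-SD 0.15 to 0.30, cut at the 30th to 70th percentile): E from 0.458 to 0.626, a loss of 37% to 54%.
- Flat, cut at its median: E = 0.75, a loss of 25%.
- Two humps (equal mixture of means 25 and 35, SDs 3 and 4, cut at 30): E = 0.741, a loss of 26%.

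**3. What this does to power.** Assume 40 patients, a true correlation of 0.4 and two-sided α = 0.05 (the plan does not state sidedness). By Fisher's z, power = Φ[atanh(r)·√(n − 3) − 1.96], with r multiplied by √E after the split.

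- Continuous: atanh(0.4) = 0.4236; 0.4236 × √37 − 1.96 = 0.617; power 73%.
- 50:50 split: r = 0.4 × 0.798 = 0.319; power 52%.
- 70:30 split: r = 0.4 × 0.759 = 0.303; power 48%.
- 80:20 split: r = 0.4 × 0.700 = 0.280; power 42%.

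With an assumed 50 patients the corresponding figures are 83%, 62%, 57% and 50%.

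**4. BMI of exactly 30.** The passages side by side:

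| Sentence | Where 30 falls |
|---|---|
| Descriptive classes | end of the 25-30 overweight class |
| Two comparison groups | neither (below 30, above 30) |
| CSF pressure limit | neither (below 30, above 30) |

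For BMI kept to one decimal, the share at 30.0 is Φ((30.05 − m)/s) − Φ((29.95 − m)/s). With an assumed mean m of 27 to 36 and SD s of 4 to 8, this is 0.3% to 1.0%. In 40 patients that is 0.1 to 0.4 of a patient.

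**5. The limit that steps at 30.** Suppose opening pressure is unrelated to BMI, is normal with mean m and SD s, and that only patients above the limit a are diagnosed. The mean among those diagnosed is m + s·φ(k)/[1 − Φ(k)], with k = (a − m)/s.

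- m = 250, s = 80: 285.8 for a = 200 and 313.8 for a = 250, a gap of about 28 mm H₂O.
- m = 300, s = 80: 316.3 and 335.8, a gap of about 19 mm H₂O.
- With s = 100 the gaps are about 29 (m = 250) and 22 (m = 300).

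So a difference of about 19 to 29 mm H₂O between the BMI groups could arise from selection alone under these assumed values.

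**The case against.** **Pearson correlation is already listed.** BMI is recorded as a number, so a continuous BMI correlation may be intended. This stands to the extent that a reader might infer BMI will be used in two groups and in no other way, and the documents do not establish that. They do state the split for comparisons and do not state a continuous analysis.

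**The main comparison does not depend on BMI.** The title sets ONSD before against ONSD after lumbar puncture, and a paired test on the same patients does not use BMI. No BMI hypothesis is named. This stands, and it confines the loss to supporting analyses.

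**Patients against controls.** A reader might infer that the split leaves BMI confounding in this comparison. The documents do not support that. No adjusted model is planned, so the split cannot be what weakens an adjustment. BMI is said to be recorded for the patients, and its collection in controls is not stated.

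**The gap at 30 has an evident reading.** The class list ends overweight at 30 and starts obese above it, which suggests that 30 is not obese. This is fair for the group labels. It still leaves both operative sentences silent on 30, including the one that sets a diagnostic limit. A reader might infer that such patients would be dropped, or placed once their pressure is known. No passage says so. A larger affected share would need BMI rounded to whole numbers, which the plan does not mention; its only rounding rule is one decimal for statistical numeric data.

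**Continuous BMI does not remove selection at the limit.** Correct. The limit would step at 30 however BMI is analysed. The documents also cite the Modified Dandy criteria and do not say outright that the limit is an entry criterion.

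**Conclusion.** The point holds as a correction to supporting analyses and to wording. Comparing patients in two BMI groups costs at least 36% of the information in BMI if BMI is normal and its effect linear. It costs more when the groups are unequal, and about 25% if BMI is flat or two-humped and cut near its middle. In an assumed 40 patients with a correlation of 0.4, power falls from 73% to 52% or 48% (50:50 or 70:30). The shape, sample size and correlation are all assumptions.

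The gap at exactly 30 is a plain inconsistency in two sentences, but it would probably reach under about 1% of patients at one-decimal BMI. The effect of the stepped limit on comparisons between BMI groups is real if that limit governs diagnosis, which the text suggests without stating it.

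It would go too far to say that the paired result before and after lumbar puncture is weakened, or that using continuous BMI would remove selection at the limit.

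**What to change.** 1. State that, within the patient group, BMI in kg/m² is analysed as a continuous variable by Pearson correlation with ONSD, ONSD change and CSF opening pressure.
2. Keep the split at 30 for assigning the CSF limit and for a descriptive table.
3. Say whether the CSF limit governs diagnosis. If it does, note beside the BMI results that any obese versus non-obese difference, or BMI-pressure relation, is partly shaped by a limit that changes at 30.
4. Reconcile the grouping sentence, the CSF-limit sentence and the 25-30 class so that a BMI of exactly 30 is assigned consistently in all three. The sponsor decides which side, before enrolment.

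**Cost.** Wording only. Patients' height, weight and BMI are already collected, Pearson correlation is already among the listed tests, and the two-group table can still be shown.

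### The plan does not mask the ultrasound reader to whether a scan is before or after lumbar puncture, so expectation could create or enlarge the before-after difference in ONSD

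*Combined protocol and SAP*

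**What the plan says.** The section Optic Nerve Ultrasonography sets out who measures and when: "Measurements will be taken from all the patients before and 10-15 minutes after the LP by a neurosonologist experienced in ONSD measurement". The same sentence contains the only masking in the plan: the reader should "have no prior information about the patients' clinical characteristics and who will not participate in the LP administration or treatment decision of the patients".

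The technique fixes some things and leaves others to the operator. ONSD is read "at 3 mm under the bulb from the sections that give the best images of the area where optic nerve enters into the globe". The border is defined as the overall sheath diameter, both eyes are measured in axial and sagittal planes, and measurements are taken twice.

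The section Lumbar Puncture Procedure gives the sequence. "After measurements will be obtained before LP, the patient will be placed in the lateral decubitus position"; after the LP the patient is returned to supine, and "Ultrasonographic measurements will be taken again 10-15 minutes after the LP administration". For controls it says: "Similarly, USG and ONSD measurements will be obtained from the control group in supine position without LP". No second control scan is described.

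The section Statistical Analyses gives one sentence on tests: "Chi square test, independent sample test, paired sample test and Pearson correlation analyses will be carried out for the evaluation of the data". Significance is set at p below 0.05. No sample size, SD, expected difference or reader repeatability is stated.

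**The concern.** Masking has to cover the contrast being tested. Here that is scan time, and the stated masking covers something else: clinical characteristics and involvement in the LP or in treatment. Staying out of the LP does not hide the fact that it has taken place.

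A reader who expects the sheath to be narrower after CSF is removed may, without intending to, choose a slightly different section or place the border slightly differently at the second scan. The first values may also be remembered. Either would move the paired differences systematically, and the planned analysis would report the movement as an effect of LP. What is at stake is the result named in the study title.

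**Working it through.** **1. What the masking covers.** The plan states no sample size or power figure, so there is nothing of its own to reproduce. The first step is to compare the text with the sources of bias.

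| Information that could influence the reading | Addressed in the plan? |
|---|---|
| Clinical characteristics | Yes |
| Involvement in the LP or in treatment decisions | Yes, the reader is excluded from both |
| Whether the scan is before or after LP | Not mentioned |
| The reader's own first values at the second scan | Not mentioned |

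No coding of images, later reading, random reading order or second reader is described. The fixed sequence (scan, positioning, LP, return to supine, scan again after 10-15 minutes) makes it reasonable to infer that the reader knows the time point. The documents do not say so.

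**2. Whether anything else in the design isolates a reading shift.** Write the mean paired difference as δ + b, where δ is the true mean change after LP and b is a systematic reading shift between the first and second scan. The paired test uses only the sum. Averaging over eyes, planes and repeat readings reduces random error but leaves b unchanged. A repeat scan in controls could have estimated the part of b due to repetition or order, but none is planned.

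**3. How a shift would act (illustration only).** Only the significance level of 0.05 comes from the documents. Everything else is assumed: a two-sided test, δ = 0, SD of paired differences 0.3, 0.4 or 0.5 mm, n = 20, 30 or 60, and b = 0.05, 0.10 or 0.15 mm in absolute value.

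The test statistic then follows a noncentral t distribution with n − 1 degrees of freedom and noncentrality λ = b√n / SD. The chance of significance is P(|T| > t₀.₉₇₅,ₙ₋₁).

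Worked case: n = 30, b = 0.10 mm, SD = 0.3 mm. λ = 0.10 × √30 / 0.3 = 1.826; the critical value with 29 degrees of freedom is 2.045; the chance of p<0.05 is 0.42.

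| n | b (mm) | SD 0.3 mm | SD 0.4 mm | SD 0.5 mm |
|---|---|---|---|---|
| 20 | 0.10 | 0.29 | 0.19 | 0.14 |
| 30 | 0.05 | 0.14 | 0.10 | 0.08 |
| 30 | 0.10 | 0.42 | 0.26 | 0.19 |
| 30 | 0.15 | 0.75 | 0.51 | 0.36 |
| 60 | 0.10 | 0.72 | 0.48 | 0.33 |

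With b = 0 every cell would be 0.05. For a fixed shift λ grows with √n, so enlarging the sample makes a false positive more likely. A simulation of 100,000 runs per setting at SD 0.3 and 0.5 mm agreed with the formula to within 0.003.

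**The case against.** The strongest reply is that the plan is silent on this point, which is not the same as stating that the reader is unmasked. It uses an experienced neurosonologist who is kept out of the LP and away from clinical information, and it standardises the measurement: a fixed 3 mm depth, a defined border, both eyes, two planes and repeat readings. For a small single-centre study one might ask only that the plan state whether time point is masked and, if it is not, report that as a limitation.

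Much of this is fair. That the reader knows the time point is inferred. The safeguards do narrow the room for a shift, and nothing in the documents shows how much room remains. The figures above carry no information about this trial: any non-zero bias is detected more often as n grows, and the calculation assumes no true change.

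The safeguards nevertheless do not exclude a shift in one direction, and the operator still selects the section and places the border. Followed as written, the plan leaves its main comparison open to expectation. A statement of limitation would disclose that but not reduce it.

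Two practical objections to masked re-reading also stand. Someone other than the reader must hold the code and set the reading order. And images selected by an unmasked operator can still carry part of a shift.

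**Conclusion.** The concern holds. The plan describes no masking of the reader to scan time, and nothing else in the design separates a reading shift from an effect of LP in the before-after comparison. That the reader would know the time point is a reasonable inference from the live, fixed sequence, not a stated fact. Whether a shift would occur, and how large it would be, cannot be judged from the documents. Under the assumed inputs at n = 30, shifts of 0.05 to 0.15 mm would raise the false-positive rate from 0.05 to between 0.08 and 0.75, depending on the shift and the SD. If LP does change ONSD, the estimate would be off by the amount of the shift. The plan should be changed on this point, but the illustration is no evidence that bias is present.

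**What to change.** - Save the section images from every scan (before LP, after LP, control) under a random code. A member of the team other than the reader holds the key and sets the reading order.
- Have the same neurosonologist measure the coded images later in random order, masked to person, time point, group and the live readings.
- Name the masked readings as the data for the paired and patient-control tests, and keep the live readings as secondary.
- State in the plan that section choice at acquisition remains unmasked, so the protection is partial.

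Images have to be stored at the time of scanning, so this must be specified before enrolment starts.

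**Cost.** No second reader and no new patient procedure are needed. The work is image storage, coding by existing staff and off-line reading time: 2 eyes × 2 planes × 2 time points = 8 measurements per patient, or 16 if each is taken twice. For an assumed 30 patients that is 30 × 8 = 240 to 30 × 16 = 480 measurements, plus those for controls, so more than one reading session may be needed.

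### Masking of the ONSD operator to group (IIH versus control) is not secured, which leaves the IIH-control difference and the normal ONSD value open to measurement bias

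*Combined protocol and SAP*

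**What the plan says.** **Where the groups come from (Patient Selection Criteria).** The IIH group is introduced as "Patients who apply to the neurology outpatient clinic", with a pre-diagnosis of IIH. Controls are people "who apply to the neurosonology unit for other complaints (dizziness, cerebrovascular accident, transient ischemic stroke, patent foramen ovale examination etc". Their purpose is stated: "In order to determine normal ONSD measurement". They are eligible if they "apply with other complaints than headaches, visual impairment or tinnitus will be included in the present study", so the presenting complaint has to be known when they are enrolled.

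**Who measures, and what is masked (Optic Nerve Ultrasonography).** "Measurements will be taken from all the patients before and 10-15 minutes after the LP by a neurosonologist experienced in ONSD measurement". This operator is to "have no prior information about the patients' clinical characteristics and who will not participate in the LP administration", and also has no part in treatment decisions. The operator picks the views that show the nerve best and marks the sheath border 3 mm below the globe, in two planes.

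**How controls are scanned (end of Lumbar Puncture Procedure).** "Similarly, USG and ONSD measurements will be obtained from the control group in supine position without LP". Nothing more is said about the operator, the setting or masking for controls.

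**Analysis (Statistical Analyses).** An independent-sample test is listed without naming the groups. IIH versus control is the natural reading. The significance level is 0.05.

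**The concern.** Group membership is tied to three visible features: the clinic that sends the person, the reason for attending, and whether an LP follows. Withholding the clinical history does not by itself hide any of them, and the plan describes nothing else that would. There is no mixed scan order, no coding of images and no masked re-measurement.

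This matters because the measurement depends on judgement at two points, the choice of image and the placing of the calipers. An operator who suspects IIH may settle on a wider border, and one who believes the person is a control on a narrower one. Such an error goes in opposite directions in the two groups, so it enlarges their difference and lowers the normal value that the controls are there to provide. A larger sample does not remove it; it only makes a spurious difference more likely to reach significance.

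**Working it through.** **Step 1. Set the text side by side.**

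| Question | IIH patients | Controls |
|---|---|---|
| Source | Neurology outpatient clinic | Neurosonology unit's own attenders |
| Basis of selection | Pre-diagnosis of IIH | Presenting complaint |
| Scan schedule | Before LP, and again 10-15 minutes after | Supine, no LP |
| Operator | Experienced neurosonologist | Not stated |
| Masking to clinical characteristics | Stated | Only by extension, through the opening word of "Similarly, USG and ONSD measurements will be obtained from the control group in supine position without LP" |
| Masking to group | Not described | Not described |

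Every feature that differs between the columns is a possible cue to group, and no procedure removes the cues. Even if the masking sentence is carried over to controls, it covers clinical characteristics and not the route or schedule by which a person reaches the scan.

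**Step 2. Which comparisons are exposed.** Let a shift *b* be added to every measurement in IIH patients relative to controls.

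- Paired before-after: (post + *b*) − (pre + *b*) = post − pre. The shift cancels.
- IIH versus control: the difference in means becomes the true difference + *b*. The shift stays.
- Normal value: whatever part of the shift falls on controls moves their mean by the same amount, at any sample size.

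**Step 3. Sensitivity of the group test.** The plan gives no ONSD SD, group size or observer error, so there is no figure of its own to reproduce. Only the 0.05 level comes from the documents; I take it as two-sided. Assumed: SD 0.5 mm, 30 or 50 per group, shift 0.1 or 0.2 mm, and no true difference.

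Standardised shift *d* = *b* / SD, so 0.1/0.5 = 0.2 and 0.2/0.5 = 0.4. Noncentrality = *d* × √(*n*/2), with 2*n* − 2 degrees of freedom. The false-positive rate is the probability that the noncentral t lies beyond the two-sided 5% critical value.

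| *n* per group | Shift | *d* | Noncentrality | Critical t | False-positive rate |
|---|---|---|---|---|---|
| 30 | 0.1 mm | 0.2 | 0.2 × √15 = 0.775 | 2.002 | 0.119 |
| 30 | 0.2 mm | 0.4 | 0.4 × √15 = 1.549 | 2.002 | 0.332 |
| 50 | 0.1 mm | 0.2 | 0.2 × √25 = 1.000 | 1.984 | 0.168 |
| 50 | 0.2 mm | 0.4 | 0.4 × √25 = 2.000 | 1.984 | 0.508 |

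With the SD varied from 0.4 to 0.7 mm and *n* from 20 to 50 per group, the rate runs from 7% to 24% for a 0.1 mm shift and from 14% to 70% for 0.2 mm.

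For scale, results are to be rounded to one decimal place. If ONSD is reported in millimetres, 0.1 mm is one reporting unit.

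**The case against.** A reader might infer that masking cannot hold and that the operator will know each person's group. The documents do not support that. They do not say who scans controls, whether the orbital scan shares a session or operator with a carotid or PFO study, or what the operator is told about an LP. A unit's records are not the same as its operator's knowledge. An operator from whom the referral reason is withheld would fit the text. This objection stands: the fault is an omission in the plan, and unmasking is plausible but not established.

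Nor does the plan explicitly promise masking for the case-control comparison. The sentence concerns patients scanned around an LP, so it would be wrong to say that the recruitment route breaks a stated promise. That also stands.

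At the first scan the IIH group has only a pre-diagnosis and the opening pressure is unknown, so the operator could at most suspect IIH. The return for a second scan cannot unmask a measurement already taken. Both points are correct, but suspicion is enough to influence where a border is placed.

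The titled comparison, before versus after LP, is untouched by a shift that depends only on group. This limits the point to the reference group and the normal value. Finally, the sizes are hypothetical: the shift has no source in the documents, and a null true difference is itself an assumption. They show sensitivity and do not estimate the actual bias.

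**Conclusion.** The point holds as a gap in the plan. Masking to group is neither stated nor described, and the two recruitment routes make it plausible that the operator infers the group. The IIH-control difference and the normal ONSD value are at risk. The amount of bias cannot be derived from the documents. The figures of about 12% to 51% are conditional on the SD, group sizes and shift assumed above, with no true difference between the groups. The stronger claim, that the operator necessarily knows the group, should not be made. The change is worth making because it is cheap, with medium confidence that the problem would arise in practice.

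**What to change.** State in the plan who scans controls and what that operator is told. Then:

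1. Save the axial and sagittal frames of every pre-LP IIH scan and every control scan without calipers, choosing frames by a fixed image-quality rule written in advance.
2. Code the frames by study number only.
3. Have the same neurosonologist measure them later in one mixed set in random order. Use these values for the IIH-control comparison and for the normal ONSD.
4. Where feasible, withhold the referral reason and the LP booking at the time of scanning.

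A mixed live scanning list would be harder to keep, because the IIH scan has to fall directly before the LP and be repeated 10-15 minutes after it.

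The cost is some coding and extra measuring time. No second reader or further patient procedure is needed. One weakness remains: frames are still chosen at acquisition by an operator who may suspect the group, so image selection is only partly masked. If none of this is done, report the IIH-control comparison as not masked to group.
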